9.4.4.2 Vital signs

Vital signs data will be summarized by presenting descriptive statistics for the absolute values and changes from baseline. All information collected will be listed by patient and abnormal values (see [Appendix 1](#)) will be flagged.

9.4.4.3 Laboratory evaluations

Laboratory data will be summarized in the same way as vital signs. In addition, shift tables based on normal ranges and incidence rates of notable abnormalities (see [Appendix 1](#)) will be presented.

Pharmacokinetics

All completed subjects with quantifiable pharmacokinetic (PK) measurements of secukinumab will be included in the pharmacokinetic data analysis. Serum concentrations will be expressed in mass per volume units. All concentrations below the limit of quantification or missing data will be labeled as such in the concentration data listings. PK concentrations will be summarized by visit and treatment group. In addition to mean, standard deviation, coefficient of variation, median and quartiles, the geometric mean and geometric coefficient of variation and n(log) will be presented.

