The adult AS and PsA secukinumab data support the proposed secukinumab study in children with similar pediatric spondyloarthritic conditions: ERA and JPsA. This study will investigate secukinumab treatment in children \geq 2 to $<$ 18 years of age with active JPsA or ERA JIA using a pediatric dose equivalent to the adult 150mg dose. To ensure children with a more SpA-like condition ([Martini 2012](#)) are not excluded, the ILAR diagnostic criteria for JPsA are modified NOT to exclude those who are:

- HLA-B27-positive male beginning after the 6th birthday;
- those who have AS, ERA, sacroiliitis with Inflammatory Bowel Disease (IBD), reactive arthritis (Reiter's syndrome), or acute anterior uveitis, or a history of one of these disorders in a first-degree relative.

This 2-year study consists of 3 parts plus a post-treatment follow-up period: The initial Treatment Period 1 will entail open-label secukinumab administered subcutaneously every week for the first 4 weeks (loading dose period) and at Week 8. Responders (minimum JIA ACR30 response) at the end of Treatment Period 1 (Week 12) will enter into Treatment Period 2 and be randomized 1:1 at Week 12 to either continue secukinumab or begin placebo in a blinded fashion every 4 weeks. Non-responders will not be dosed and will undergo an end of study visit on the same day and enter the Post-treatment follow-up period. Treatment Period 2 will continue until 33 patients experience a disease flare (as per American College of Rheumatology (ACR) flare definition). Patients experiencing a flare and those who remain (in

Treatment Period 1 or 2) when Treatment Period 2 completes will enter Treatment Period 3 to receive open-label secukinumab every 4 weeks until week 100. A total study duration of 104 weeks at the patient level is reached. A Post-treatment follow-up visit is performed 12 weeks after last study treatment administration for all patients unless the patient enters the extension trial.

All patients who successfully complete the study (104 weeks) will be eligible to continue secukinumab treatment in an extension trial.

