3.1 Study design

This is a double-blind, placebo-controlled, event-driven randomized withdrawal study to investigate the efficacy and safety of secukinumab treatment in the JIA categories of JPsA and ERA. The study is divided into 3 parts (plus a post-treatment follow-up period) consisting of open-label, single-arm active treatment in Treatment Periods 1 and 3 and a randomized, double-blind, placebo controlled, event-driven withdrawal design in Treatment Period 2, as described below:

Treatment Period 1: A maximum 8-week screening period is used to assess patient eligibility. All eligible patients will enter Treatment Period 1 to receive 12-weeks of open-label secukinumab at a dose predicted to achieve secukinumab serum levels equivalent to adults administered a 150 mg dose regimen (see [Section 3.3](#) for details). Secukinumab will be administered subcutaneously (s.c.) weekly for the first 4 weeks (Baseline, Weeks 1, 2, 3, 4) and then every 4 weeks thereafter. Clinical response (JIA ACR 30) will be assessed at Week 12. Responders will advance to Treatment Period 2 and non-responders must exit the trial (early termination visit and enter into the Post-treatment follow-up period).

Treatment Period 2: Patients with a clinical response (JIA ACR30) at Week 12 will enter double-blind withdrawal Treatment Period 2 to be randomized 1:1 to either secukinumab or placebo on that visit. Treatment Period 2 is event driven and will close when 33 patients experience a disease flare as per JIA definition ([Appendix 8](#)). If Treatment Period 2 is closed when a patient becomes eligible to enter Treatment Period 2, the patient will skip Treatment Period 2 and advance directly to Treatment Period 3. When the 33rd flare is observed, all investigators will be informed that Treatment Period 2 is closed and all remaining patients will enter Treatment Period 3 at their next scheduled visit. Because Treatment Period 2 is event driven, it is possible that a patient remains in Treatment Period 2 for the duration of the study (Week 104) before 33 disease flares are observed. Such patients will complete the study without having entered Treatment Period 3.

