Treatment Period 3: Patients experiencing a disease flare in Treatment Period 2 will immediately enter Treatment Period 3 to receive open label secukinumab every 4 weeks until total study duration of 104 weeks for that patient is achieved. Additionally, when Treatment Period 2 closes, all remaining patients in Treatment Period 2 will enter Treatment Period 3 at their next scheduled visit and all remaining Treatment Period 1 patients who become eligible to enter Treatment Period 2 will skip Treatment Period 2 and enter Treatment Period 3 directly. Consequently, the starting time point of Treatment Period 3 for each patient may be different.

Post-treatment follow-up: All patients completing the study (Week 104) or who discontinue early will enter the Post-treatment follow-up period lasting 12 weeks from the last study drug dose administration. Only patients who qualify and enter the secukinumab extension trial without interruption of secukinumab treatment will not require this Post-treatment follow-up visit.

Due to the event driven design of Treatment Period 2, the lengths of Treatment Periods 2 and 3 will be variable and patient-specific. Based on the study design, a patient may participate in:

1. **Treatment Period 1 only** if the patient is a non-responder at the end of Treatment Period 1 and must discontinue from the study.
2. **Treatment Periods 1, 2, and 3.**
3. **Treatment Periods 1 and 2 only** if the patient never experiences a disease flare after randomization into Treatment Period 2 and reaches a total study duration of 104 weeks before a total 33 flares in Treatment Period 2 are observed.
4. **Treatment Periods 1 and 3 only** if 33 flares are observed in Treatment Period 2 prior to or at the time the patient reaches Week12 (end of Treatment Period 1) and is eligible to enter Treatment Period 2. In this situation, the patient will enter Treatment Period 3 directly from Treatment Period 1 to receive open-label secukinumab.

All patients will participate in the Post-treatment follow up period, except for those entering the extension study.

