5.2 Treatment arms

Patients will enter Treatment Period 1 to receive 12-weeks open label active treatment of either s.c. secukinumab 75 or 150 mg, based on their body weight (< 50 kg or ≥ 50 kg) at each dosing visit starting at Baseline. They will receive further doses at Weeks 1, 2, 3, 4, and 8.

At the End of Treatment Part 1 visit at Week 12, efficacy assessments must be performed and ACR response criteria evaluated to determine future patient disposition in the study. Patients who are assessed as a responder (minimum JIA ACR30 response) will enter Treatment Period 2 at that same visit to be randomized to either continue their active treatment or matching placebo every 4 weeks, in a blinded manner, in a 1:1 ratio until 33 patients experience a disease flare and Treatment Period 2 is completed. If Treatment Period 2 is closed at the time of the Week 12 visit, the patient will skip Treatment Period 2 and enter Treatment Period 3 directly to receive open-label secukinumab. Patients who are not a responder at the Week 12 visit will have the early termination visit done on the same day and enter into the Post-treatment follow-up period at that visit without receiving any further study drug administration.

Patients will enter Treatment Period 3 from Treatment Period 2 because of either experiencing a flare or when 33 flares in Treatment Period 2 are overall observed and Treatment Period 2 is closed. Patients in Treatment Period 1 when Treatment Period 2 closes will skip Treatment Period 2 and advance directly into Treatment Period 3 after successfully completing Treatment Period 1. During Treatment Period 3, patients will receive open-label secukinumab (either 75 or 150 mg, based on body weight) every 4 weeks until study Week 100 is reached.

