5.6 Study Completion and Discontinuation

5.6.1 Study completion and post-study treatment

A patient will be considered to have completed the study when the patient has received a maximum of 104 weeks of study treatment and completed all of the scheduled study assessment and procedures up to and including the Week 112 visit. All patients who complete the scheduled study assessments and procedures up to and including Week 104 will be eligible to enter an extension trial to continue secukinumab treatment without interruption. Patients who enter the extension study will be considered study completers at Week 104 and the follow-up visit at Week 112 will not be performed.

Information on the subject's completion or premature discontinuation of the study and the reason for discontinuation of the study will be recorded on the appropriate eCRFpage. Additionally, the investigator or site staff must contact the IRT as soon as possible to record the subject's study completion and/or discontinuation.

The Investigator must provide follow-up medical care for all subjects who are prematurely withdrawn from the study, or must refer them for appropriate ongoing care. This care may include initiating another treatment outside of the study as deemed appropriate by the investigator. This treatment may be any non-biologic DMARD. In case of a biologic treatment, a waiting period of 3 months before initiating the treatment is recommended.

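### The PK analysis is based on completed subjects without saying what was completed; on the protocol's only patient-level definition, Week-12 non-responders fall out of a Treatment Period 1 objective

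*Protocol*

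**What the plan says.** The inclusion rule stands under the Pharmacokinetics subheading of protocol Section 9.4.4.3: "All completed subjects with quantifiable pharmacokinetic (PK) measurements of secukinumab will be included in the pharmacokinetic data analysis". Section 9.1 defines analysis sets period by period but has no PK set, so it does not settle what the rule means.

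Section 5.6.1 is the one place that says when a patient has completed: "A patient will be considered to have completed the study when the patient has received a maximum of 104 weeks of study treatment" and has gone through all scheduled assessments up to Week 112. It adds: "Patients who enter the extension study will be considered study completers at Week 104". Two other places use the word in the same sense. Section 1.1 has "All patients who successfully complete the study (104 weeks) will be eligible to continue secukinumab treatment in an extension trial", and Section 3.1 sets completion against early discontinuation: "All patients completing the study (Week 104) or who discontinue early will enter the Post-treatment follow-up period".

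On Week-12 non-responders, Section 3.1 says "Responders will advance to Treatment Period 2 and non-responders must exit the trial". Its list of possible patient paths gives Treatment Period 1 only "if the patient is a non-responder at the end of Treatment Period 1 and must discontinue from the study".

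Period-level wording also occurs. Section 5.2 has patients "advance directly into Treatment Period 3 after successfully completing Treatment Period 1", and Sections 3.1 and 3.5 time the PK interim analysis by completion of the Week 12 visit.

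The third secondary objective (Section 2.2) is to evaluate PK and confirm the predicted dose in Treatment Period 1. Table 2-1 gives the same timeframe. Section 6.6.2 takes PK samples in all subjects, and Table 6-5 marks Weeks 0, 2, 4, 8 and 12 as required in every subject.

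**The concern.** The objective asks about exposure over 12 weeks in children treated with the predicted dose. If *completed* carries the only meaning the protocol defines for a patient, the summary of those 12 weeks is taken from patients selected on two later outcomes: response at Week 12, and staying in the study for about two years. It would then not describe exposure in everyone treated, and required samples from the excluded children would go unused. If *completed* means the first 12 weeks, the loss is much smaller, but it still falls on patients who stopped early and have valid concentrations. Two analysts following the sentence in good faith could build PK sets that differ by all non-responders and all later leavers.

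**Working it through.** **Step 1: reproduce the protocol's own figure.** Inputs: a minimum of 60 patients in Treatment Period 2 (Sections 4 and 9.6) and a response rate of 70% to 85% (Section 9.6). Patients to treat = 60 / response rate.
- 60 / 0.85 = 70.6 (the protocol states 70)
- 60 / 0.70 = 85.7 (the protocol states 86)

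The stated range of 70 to 86 reproduces with no allowance for dropout before Week 12. No Treatment Period 1 dropout rate can therefore be read back from it.

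**Step 2: can a Week-12 non-responder be a completer under Section 5.6.1?** The word maximum in that section's first condition sets no minimum duration. The second condition requires the scheduled assessments to Week 112, or to Week 104 for extension entrants. Non-responders have an early termination visit at Week 12, receive no further drug, and are followed only to 12 weeks after their last dose. They cannot meet it.

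**Step 3: loss on the study-completion reading.** Non-responders = patients treated × (1 − response rate).
- 70 × 0.15 = 10.5 (15%)
- 86 × 0.30 = 25.8 (30%)

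Required Treatment Period 1 concentrations after the first dose are at Weeks 2, 4, 8 and 12, so four per patient. If every sample is obtained:
- 4 × 10.5 = 42 of 4 × 70 = 280
- 4 × 25.8 = 103 of 4 × 86 = 344

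At the planned enrolment of about 80 (Section 4), 80 − 60 = 20 patients (25%) would not reach Treatment Period 2. The protocol does not split these between non-response and dropout.

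Later leavers add to the loss. The protocol gives no rate for them. Purely as an assumption, 10% to 20% attrition among 60 responders would leave 60 × 0.90 = 54 to 60 × 0.80 = 48 patients in the PK analysis.

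**Step 4: loss on the Week-12 reading.** Non-responders assessed at Week 12 stay in. Only patients who stop earlier are lost, and their number is not given. As a scale only, each 5% stopping early would be 0.05 × 70 = 3.5 to 0.05 × 86 = 4.3 patients.

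**Step 5: does the interim analysis cover the gap?** The PK interim analysis (Sections 3.1, 3.5 and 9.5) is not tied to study completion. It is run after the Week 12 visit in the first 10 patients per weight group, it allows patients who discontinue before Week 12 to be replaced, and it may be waived if other pediatric secukinumab data suffice. It is separate from the summaries in Section 9.4.4.3 and does not repair their inclusion rule.

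**The case against.** The strongest reply is that a two-year completer filter was probably never meant. Section 5.6.1 defines completion of the study and does not mention the PK analysis. Where the protocol's PK text names a completion milestone, it is the Week 12 visit, which suits a Treatment Period 1 objective. Taking samples from all subjects, adding samples at flare visits, and summarizing concentrations by visit and treatment group also fit poorly with a filter at Week 104 or 112. The sentence says that completed subjects are included; it does not say that only they are. Finally, the protocol's described method for confirming the dose is the model-based interim comparison in Section 9.5, not these descriptive summaries.

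Much of this stands. The Week-12 reading is plausible, and the 15% to 30% loss depends on rejecting it. The missing word *only* carries less weight, because a sentence that states who enters an analysis is ordinarily read as defining its population. The reply also does not clear the sentence: Section 9.4.4.3 does not state the Week-12 meaning, and even that meaning leaves out patients who stop earlier with usable concentrations. The interim comparison is small and may be waived.

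Leaving the matter to the SAP is not a full answer either. The protocol has stated a rule, and an SAP that included all treated patients would depart from it.

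**Conclusion.** The point holds as a minor one: a stated inclusion rule uses a term with two workable meanings, and neither suits the Treatment Period 1 objective. On the defined meaning, about 10 to 11 of 70 up to about 26 of 86 treated patients are lost through non-response, plus an unknown number of later leavers. On the Week-12 meaning, the loss is confined to patients who stop before Week 12, a number that cannot be derived. The first figures rest on the protocol's assumed response rates and on the study-completion reading.

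A reader might go further in three ways that the document does not support:
- That the protocol definitely excludes non-responders. The Week-12 reading is open, so the exclusion is conditional.
- That the PK results or the dose confirmation will be biased. Nothing in the protocol relates exposure to response or retention in this population, so neither size nor direction can be derived.
- That the interim dose check either shares the two-year filter or is free of any completion condition. It is not tied to study completion, but it follows the Week 12 visit and permits replacement of earlier discontinuations.

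The analysis is descriptive and secondary, and the primary time-to-flare analysis is unaffected.

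**What to change.** Replace the inclusion sentence in Section 9.4.4.3 with wording such as:

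> The PK analysis comprises every patient who received at least one dose of secukinumab and has at least one valid post-dose concentration measurement, regardless of response and of study or period completion.

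The SAP's PK set should carry the same definition. How values below the quantification limit enter the summaries is ordinary SAP detail and needs no change here.

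The cost is one sentence. No visits or blood draws are added, because the Treatment Period 1 samples are already required from every patient.

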9.5 Interim analyses

A PK interim analysis is planned at the end of Treatment Period 1 in the first 10 patients enrolled in each weight category (< and \geq 50kg) in order to confirm the predicted doses. This will be done by using previously developed population PK model [\[AIN457 in RA – Population PK modeling report\]](#) and comparing predicted individual PK profiles with actual PK observations (e.g., superimposing the data with simulations from the model). Only Treatment Period 1 PK data for these patients will be included in this interim analysis thus Treatment Period 2 data will remain blinded. No alpha level adjustment will be necessary.

The PK interim analysis for both weight category subgroups may not be necessary if data from currently ongoing pediatric psoriasis study is available.

Novartis will perform the primary efficacy analysis of Treatment Period 2 (time to flare) when Treatment Period 2 is completed. No alpha level adjustment will be necessary.

Interim safety review

The DMC will review unblinded safety data as described in [Section 8.4](#). These results will only be available to DMC members and the independent statistician and statistical programmer who will generate the output for DMC review. All unblinded individuals will keep results confidential up to final clinical data base lock and unblinding.

9.6 Sample size calculation

It is assumed that the Flare-free time follows an exponential distribution with a constant hazard ratio.

The hazard ratio of flare events for the secukinumab group relative to placebo group is estimated to be 0.32 in Treatment Period 2. The hazard ratio of 0.32 was used to establish the sample size necessary in Treatment Period 2 and consequently Treatment Period 1 (derived from the median time to disease flare for ETANERCEPT and placebo in LOVELL et. al. 2000). With the hazard ratio assumed to be 0.32, 33 flares are necessary to detect a statistically significant difference between secukinumab and placebo assuming 90% power and a 1-sided significance level of 0.025. No data is available to estimate the placebo hazard rate beyond 6-months. Given that uncertainty and a maximum 21-month follow-up in Treatment Period 2, the total sample size necessary to achieve 33 flares in Treatment Period 2

is estimated to be at least 60 and at most 80 patients. Assuming approximately 70% to 85% of patients respond in Treatment Period 1, the estimated minimum number of patients treated in Treatment Period 1 is between 70 and 86. Under the assumption of 12 months of accrual duration, the total maximum expected study duration is 33 months. The expected number of flare events is 12 and 21 respectively for secukinumab and placebo group in Treatment Period 2.

10 Ethical considerations

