5.3 Treatment assignment and randomization

All patients fulfilling all entry criteria will be assigned to AIN457/secukinumab 75 or 150 mg, based on body weight (< 50 kg or ≥ 50 kg) and continue to receive an appropriate secukinumab dose at each visit based on their weight at that visit. At the Week 12 visit, all responders will be eligible to enter Treatment Period 2 where they will be randomized via Interactive Response Technology (IRT) to one of the two treatment arms, active as secukinumab 75 or 150 mg, or matching placebo based on their weight at that visit.

In Treatment Period 2, patients will be randomized by each JIA category (strata: JPsA and ERA) in a 1:1 ratio to receive AIN457 or placebo so that approximately an equal number from each category will receive either active or placebo.

At each subsequent dosing visit body weight will be checked and the patients will be assigned the correct blinded dose based on their weight at that visit.

The Investigator or his/her delegate will contact the IRT after confirming that the patient fulfills the response criteria. The IRT will assign a randomization number to the patient, which will be used to link the patient to a treatment arm and will specify a unique medication number for the first package of study drug to be dispensed to the patient. The randomization number will not be communicated to the caller.

The randomization numbers will be generated using the following procedure to ensure that treatment assignment is unbiased and concealed from patients/parents and Investigator staff. A patient randomization list will be produced by the IRT provider using a validated system that automates the random assignment of patient numbers to randomization numbers. These randomization numbers are linked to the different treatment arms and to study strata, which in turn are linked to medication numbers. A separate medication list will be produced by or under the responsibility of Novartis Drug Supply Management using a validated system that automates the random assignment of medication numbers to packs containing the investigational drug(s).

The randomization scheme for patients/subjects will be reviewed and approved by a member of the Randomization Group.

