9.4 Analysis of the primary variable(s)

9.4.1 Variable(s)

The primary efficacy endpoint will be time to disease flare event in Treatment Period 2, which is defined as the interval between the date of randomization to the date of first occurrence of disease flare event. The analysis of the primary efficacy endpoint will be based on the FAS Treatment Period 2.

All subjects who enter Treatment Period 2 will be followed until the sooner of either experiencing a disease flare or the end of Treatment Period 2 when 33 flare events are observed. Subjects who have not experienced flare event at the end of Treatment Period 2 data (as defined in [Section 3.1](#)) or discontinue prematurely from Treatment Period 2 before it closes for reasons other than experiencing a disease flare will be censored at the date of the last efficacy evaluation in Treatment Period 2.

Statistical model, hypothesis, and method of analysis

The primary objective for Treatment Period 2 of the study is to show superiority of secukinumab over placebo regarding the primary variable in Treatment Period 2.

The following statistical hypothesis will be tested once the required number of flares has been observed and the study has been stopped:

$$H_0: 1 - S_{AIN}(t) \geq 1 - S_{Pla}(t)$$

$$H_A: 1 - S_{AIN}(t) < 1 - S_{Pla}(t)$$

at each time point t , with $S_{AIN}(t)$ and $S_{Pla}(t)$ being the survivor functions in the secukinumab and placebo treatment group at time t .

The two treatment groups will be compared using a one-sided stratified Logrank test with the stratification factor of JIA category (ERA or JPsA) at the 2.5% level of significance. Hazard ratios and their associated 95% confidence intervals will be estimated based on a Cox proportional hazards model with treatment and stratification factor as explanatory variables.

The Kaplan-Meier estimates of the proportion of patients with the flare event at selected landmark points, along with its 95% confidence intervals using Greenwood's formula, will be provided. The primary analysis will be based on the FAS for Treatment Period 2.

Handling of missing values/censoring/discontinuations

All patients in Treatment Period 2 will have a value of time to flare either by having an event or being censored.

Supportive analyses

For sensitivity purposes, the primary analysis will be repeated using an unstratified log-rank test.

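### The 90% power stated for 33 flares is the Schoenfeld approximation; the planned stratified log-rank test has about 87–88% by simulation

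*Protocol*

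**What the plan says.** Protocol section 9.6 sets the event target of Treatment Period 2. Its model is: "It is assumed that the Flare-free time follows an exponential distribution with a constant hazard ratio". Its effect size is: "The hazard ratio of flare events for the secukinumab group relative to placebo group is estimated to be 0.32 in Treatment Period 2". From these it concludes that "33 flares are necessary to detect a statistically significant difference between secukinumab and placebo assuming 90% power and a 1-sided significance level of 0.025".

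The same section puts the number randomized at 60 to 80, with 12 months of accrual and "a maximum 21-month follow-up in Treatment Period 2". It expects 12 flares on secukinumab and 21 on placebo. It names no event-count formula and gives no placebo hazard rate.

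Section 9.4.1 fixes the primary analysis as a "one-sided stratified Logrank test with the stratification factor of JIA category" at the 2.5% level. Section 5.3 fixes the allocation: "patients will be randomized by each JIA category (strata: JPsA and ERA) in a 1:1 ratio to receive AIN457 or placebo". Section 4 aims for at least 20 randomized patients per category but does not set the mix. Section 3.2 describes the study as adequately powered.

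**The concern.** The Schoenfeld formula takes the log-rank information as D/4, where D is the number of flares. That is accurate when the hazard ratio is near 1 and both arms stay about equally at risk. At a hazard ratio of 0.32 the placebo arm loses patients to flare much faster, the flares split unevenly, and the information falls below D/4. With only 33 flares, the large-sample approximation itself is also strained. Section 9.6 forecasts the uneven split but quotes the power that belongs to an even one.

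At stake is a stated design property. If the true effect is the planned one, the chance of missing it is about 12–13% rather than 10%.

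**Working it through.** **Inputs.** From section 9.6: HR 0.32, one-sided alpha 0.025, 90% power, 33 flares, exponential times, N = 60 to 80, 12-month accrual, 21-month cap, expected split 12/21. From 5.3: 1:1 allocation within category. From 9.4.1: log-rank test stratified by JIA category. Constants: ln(0.32) = −1.139, z for 0.025 = 1.960, z for 90% power = 1.282.

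**Step 1. Reproduce the plan's figure (Schoenfeld).**
- Flares needed: 4 × (1.960 + 1.282)² / 1.139² = 32.4, rounded up to 33.
- Power at 33: Φ(√(33/4) × 1.139 − 1.960) = Φ(1.31) = 90.5%. At 32 flares it would be 89.7%.

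The stated count is therefore correct by this formula.

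**Step 2. Use the protocol's own flare split.** Replace D/4 = 8.25 by 12 × 21 / 33 = 7.64.
- Power: Φ(√7.64 × 1.139 − 1.960) = Φ(1.19) = 88.3%.

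**Step 3. Compare another standard formula (Freedman).**
- Flares needed: (1.32/0.68)² × (1.960 + 1.282)² = 39.6, so 40. Power at 33 flares is 84.1%.

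The two textbook formulas lie either side of the simulated values below.

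**Step 4. Simulate the planned test.** Exponential flare times, HR 0.32, uniform 12-month accrual, 21-month cap, stop at the 33rd flare, no dropout, 20,000 trials per setting (standard error about √(0.875 × 0.125/20,000) = 0.23 points). The protocol gives neither the placebo median nor the category mix, so both are assumed. Selected results, with equal hazards in the two categories:

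| N | Placebo median (months) | Category mix | Mean flares, secukinumab/placebo | Stratified | Unstratified |
|---|---|---|---|---|---|
| 60 | 2 | 1:1 | 12.0/21.0 | 87.3% | 88.6% |
| 60 | 2 | 2:1 | 12.0/21.0 | 87.0% | 88.2% |
| 70 | 3 | 1:1 | 11.0/22.0 | 87.4% | 88.4% |
| 70 | 6 | 2:1 | 10.3/22.7 | 88.0% | 88.8% |
| 80 | 6 | 1:1 | 10.0/23.0 | 88.1% | 88.7% |
| 80 | 9 | 2:1 | 9.9/23.1 | 88.3% | 88.6% |

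- Over all settings with placebo medians of 2 to 9 months, the range is 87.0–88.3% stratified and 88.1–88.8% unstratified. A separate simulation with 40,000 trials per setting and medians of 2, 4, 6 and 8 months gives 86.8–88.3% stratified.
- N = 60 with a 2-month placebo median reproduces the protocol's 12/21 split and gives 87.0–87.3% stratified.
- With a 1-month placebo median, stratified power falls to 85.7–86.1%.
- If one category has twice the hazard of the other (6-month setting), the stratified test gives about 87.5% and the unstratified 86.1–86.7%.
- Simulated type I error is about 2.5–2.8%, so the lower power does not come from a conservative test.

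**Step 5. Divide the gap.** At N = 60, median 2 months, 1:1 mix: 90.5% (formula) to 88.6% (unstratified) is 1.9 points, and 88.6% to 87.3% (stratified) is 1.3 points. At N = 80, median 6 months, 1:1 mix, the parts are 1.8 and 0.6 points. In both settings the approximation is the larger part.

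**Step 6. Flares for a simulated 90%.** At 35 flares the stratified test gives 89.5–89.6% (N = 70, median 3 months; N = 80, median 6 months). At 36 it gives 90.1–90.7%.

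**The case against.** The strongest reply is that nothing is miscalculated. Schoenfeld is a standard event-count formula, 33 is its correct answer from the stated inputs, and the protocol does not claim a simulated power. This stands. A reader might infer an arithmetic error from the gap, but the documents do not support that: the figure reproduces exactly.

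A second reply is that the placebo medians and category mixes are assumptions of this check. Section 9.6 says that no data exist to estimate the placebo hazard beyond six months, and section 4 sets only a target minimum per category. This stands too, so the simulated figure cannot be called the power under the protocol's own assumptions alone. It is not very sensitive to them, however, and no setting tried reaches 90% at 33 flares. The 88.3% in step 2 needs neither assumption, only the protocol's own 12/21 split.

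Third, one might blame stratification. That is mostly unfounded: the unstratified test also misses 90%, and when the categories differ in hazard the stratified test is the more powerful of the two.

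Finally, the gap is small beside the uncertainty in the hazard ratio, which 9.6 derives from one earlier etanercept study. By the Schoenfeld formula at 33 flares, HR 0.35 gives about 85% power and HR 0.40 about 75%. That is a fair reason to rate the point as minor. It is not a reason to leave the figure unqualified.

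**Conclusion.** The point holds as a minor correction to a stated design property. At 33 flares and HR 0.32, the planned stratified log-rank test has about 87–88% power, 2 to 3 points below the stated 90%. The main cause is a large-sample formula applied at an extreme hazard ratio with few events, and stratification adds a smaller part. The result rests on exponential times, a constant hazard ratio, no dropout, placebo medians of 2 to 8 months and category mixes of 1:1 or 1:2. A placebo median near 1 month would lower it to about 86%.

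A reader might go further and infer that the trial is inadequately powered or that the flare target is invalid. The documents do not support that. Power of 87–88% at the planned effect is still substantial, type I error is close to its nominal level, and 33 is a legitimate Schoenfeld count.

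**What to change.** Keep 33 flares, the enrolment plan, the test and the significance level. Amend section 9.6 to say three things:

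- the 90% for 33 flares at HR 0.32 and one-sided 2.5% is the Schoenfeld approximation;
- by simulation, the planned stratified log-rank test has about 87–88% power;
- which placebo hazard and category mix the simulation assumes.

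The cost is a sentence or two in 9.6 and a slightly less favourable figure; conduct does not change. If the sponsor wants a simulated 90%, about 36 flares would be needed, but that changes the design and is not required to correct the text.
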